### **Risks and Benefits:**

Usual care participants may be at higher risk for complications associated with elevated blood pressure, especially if they do not establish care with a primary provider. However, this is not more risk than what occurs typically. In fact, they will be offered a standard of care hospital follow up visit with the clinic and with 6 month study blood pressure assessments, usual care patients may have more MD contact, and opportunities for referral to primary care, than typical.

There is potential for adverse effects associated with aggressive blood pressure reduction. We have chosen a conservative and currently AHA recommended BP goal and will monitor for hypotension, syncope, and falls that may result from hypotension. These are included these as safety outcomes.

Participants may be burdened by numbers of surveys and telephone calls. We will give breaks and minimize number of forms requested to obtain necessary data. Telephone calls will be brief.

Another potential risk of this study is breach of confidentiality. This risk will be minimized with confidentiality measures described below.

All patients, including usual care group, may benefit from ambulatory blood pressure assessments and communication with primary care providers about risk factor goals. More patients will be given access to specialty care (uninsured and underinsured) than would be typically.

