## Intervention

Components of the telehealth intervention will target behaviors associated with racial disparities (African American focused) in BP control. At the time of discharge, intervention patients will receive a package containing an iPad (with a data plan) and a blue tooth enabled blood pressure monitor that allows automatic transmission of encrypted BP data to the study team (QardioARM). Patients will be allowed to use their own smart device if it is compatible with the BP device). Patients and/or caregivers will be instructed in use of equipment and the first video telehealth visit will be arranged. They will complete questionnaires including a depression screen, a dietary assessment, a cognitive screen, and a sleep apnea screen prior to discharge. Patients will receive a phone call at 72 hours by the discharge nurse navigator or social worker (standard of care) to assure that they have received their medications and follow-up appointments. The first telehealth visit will occur 7 days after discharge. A stroke prevention-trained nurse practitioner (**NP**) or **MD**, social worker (**SW**), and pharmacist will attend this video telehealth visit. The NP will review the participant's hospital records and depression, dietary, and sleep apnea screens, will reinforce the care plan based on patient-specific needs. The NP or MD will counsel patients on salt reduction, the Mediterranean diet, and the importance of diet and exercise for stroke prevention. The NP (or MD) and pharmacist will review the BP data to determine the need for medication adjustment. The pharmacist will discuss side effects and

interactions. Treatment of hypertension and selection of BP lowering medications will be in accordance with latest published guidelines for BP management. The SW will assess the need for medication assistance and other resources. The care plan will be shared with primary care providers (PCP) and patients will be referred to a PCP if they do not have one. The SW will assist uninsured patients in applying for Texas County Indigent Care programs.

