Participants will be prompted to transmit BP logs through the telemonitoring device every 2 weeks until average BP is < 130/80, then monthly thereafter. Uncontrolled BP will prompt a call from the pharmacist to discuss medication adherence and the need for further titration. Subsequent video telehealth visits for intervention patients will be attended by the NP (or MD) and pharmacist 1 month, 3 months, and 5 months after enrollment. Care plans will be reviewed and medication and lifestyle adherence will be assessed. Medications will be adjusted as appropriate. Participants will complete electronic health care utilization and recurrent vascular CRFs using the iPad at 3 months and 6 months (final outcome). Participants will receive educational messaging once every other week throughout the study period. Messages will be sent to the participants' cellular phones. The messages will contain one of the following: a reminder to monitor BP, information from about lifestyle and diet for BP reduction, or a message from the pharmacist about medication adherence. Final outcome assessments (detailed below) will occur at 6 months.

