#### **Usual Care (Control) Group**

Participants randomized to usual care will complete questionnaires including a depression screen, a dietary assessment, a cognitive screen, and a sleep apnea screen prior to discharge. A summary of the assessments will be given to the patient and they will be instructed to follow-up with their PCP and to monitor their BP. They will be contacted by the discharge nurse navigator or social worker at 72 hours to as per usual care to determine if they have received their medication and made their appointments. They will be offered a standard of care hospital follow up appointment with a stroke neurologist or nurse practitioner at the clinic. The RC will contact participants at 30-days, 90-days, 150-days to encourage continued participation. The RC will complete a telephone CRFs to obtain information about readmissions, hospital visits, and recurrent vascular events at 30 days and 90 days. Final outcome assessments (detailed below) will occur at 6 months.

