## **Primary Clinical Outcomes**

The primary clinical outcome will be the daytime ambulatory systolic blood pressure at 6 months. Secondary clinical outcomes will include the following: daytime ambulatory diastolic blood pressure, nighttime ambulatory systolic and diastolic blood pressure; BMI at 6 months; recurrent vascular event rate (stroke, myocardial infarction, acute cardiac death); and acute healthcare utilization rate (hospital readmission and acute care visits to emergency room and/or urgent care). The 6- month behavioral outcomes will include change in self-efficacy for taking medication as prescribed, medication adherence, and caregiver burden. Patient satisfaction will be assessed using scores obtained from the Patient Telemedicine Satisfaction Survey.

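### Hypotension, syncope and falls are called safety outcomes, but the plan describes no common way to ascertain or tabulate them in the two arms

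*Combined protocol and SAP*

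**What the plan says.** Risks and Benefits acknowledges that lowering blood pressure aggressively may cause harm. Besides a conservative target, its answer is that the investigators "will monitor for hypotension, syncope, and falls that may result from hypotension. These are included these as safety outcomes". It gives no definition, form or schedule.

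Primary Clinical Outcomes lists ambulatory pressures, BMI, "recurrent vascular event rate (stroke, myocardial infarction, acute cardiac death); and acute healthcare utilization rate", behavioural measures and satisfaction. Acute healthcare utilization there includes emergency room and urgent care visits.

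Follow-up before month 6 differs by arm.

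- **Intervention:** "Participants will be prompted to transmit BP logs through the telemonitoring device every 2 weeks", then monthly once the average is controlled. "The first telehealth visit will occur 7 days after discharge". Later video visits are attended by the "NP (or MD) and pharmacist 1 month, 3 months, and 5 months after enrollment". For events, "Participants will complete electronic health care utilization and recurrent vascular CRFs using the iPad at 3 months and 6 months (final outcome").
- **Usual Care (Control) Group:** "The RC will contact participants at 30-days, 90-days, 150-days to encourage continued participation". Two of these three contacts also carry an event form, described as follows: "The RC will complete a telephone CRFs to obtain information about readmissions, hospital visits, and recurrent vascular events at 30 days and 90 days". These patients are advised to monitor their own pressure, but no reading is described as reaching the study before the 6-month ambulatory recording.

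**The concern.** The monitoring promised under Risks and Benefits is part of the protocol's stated protection against over-treatment. If it has no definition, collection procedure or tabulation, the trial cannot say whether hypotension, fainting or falls were more frequent with the intervention than with usual care.

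Unequal contact adds to this. A table assembled from whatever each arm's procedures happen to reveal would compare the procedures as much as the patients. Aim 2a is to examine the suitability of outcome measures for a larger trial. For these three outcomes the plan describes no common measure to examine.

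**Working it through.** There is no stated figure to reproduce: the 50 + 50 patients are set by feasibility.

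**1. Where the three outcomes appear**

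| Section | Content | Any of the three named? |
|---|---|---|
| Risks and Benefits | Declares them safety outcomes | Yes, without definition, form or schedule |
| Primary Clinical Outcomes | Blood pressure, BMI, vascular events, acute utilization, behaviour, satisfaction | No |
| Outcome Assessments | 24-hour ambulatory recording, BMI, utilization and vascular event forms, questionnaires | No |
| Sample Size Estimation and Statistical Approach | Completion, satisfaction, primary model, named secondary analyses | No |

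**2. Described ascertainment before month 6**

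Transmissions: 26 weeks / 2 = 13, but the 13th falls at week 26 itself, so 12 if pressure is never controlled. If it is controlled at the first log, 1 + about 5 monthly = about 6. Video visits: 1 (day 7) + 3 (months 1, 3, 5) = 4.

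| Source | Intervention | Usual care |
|---|---|---|
| Prompted transmissions to the study | about 6 to 12 | 0 |
| Study clinician video visits | 4 | 0 |
| Scheduled coordinator contacts | none described | 3 (days 30, 90, 150) |
| Event forms | 1 (month 3, iPad) | 2 (days 30 and 90, telephone) |

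Visits review transmitted readings, so the first two rows overlap and should not be added. Both arms have the 72-hour call and the 6-month assessment.

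**3. What this implies by event type**

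Let p be the true risk, equal in both arms, and h the share of events that lead to a hospital visit. Let d_I and d_C be the detection probabilities for those events, and q_I and q_C those for the rest. The false difference (intervention minus usual care) is

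p × [h(d_I − d_C) + (1 − h)(q_I − q_C)].

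The documents give none of these inputs. All values below are assumed, to show how far the answer moves.

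- *Hypotension seen only through telemetry* (h = 0, q_I = 0.9, q_C = 0): 0.05 × 0.9 = +4.5 points at 5% risk, and 0.30 × 0.9 = +27 points at 30%.
- *Mixed events, hospital-treated ones fully seen in both arms, others in the intervention arm only* (d_I = d_C = 1, q_C = 0): low case (p 5%, h 50%, q_I 25%) 0.05 × 0.5 × 0.25 = +0.6 points; central case (10%, 25%, 50%) 0.10 × 0.75 × 0.5 = +3.75 points, or 3.1 against 1.25 patients of 50; high case (20%, 10%, 75%) 0.20 × 0.9 × 0.75 = +13.5 points. This version cannot go negative, because it gives extra detection to one arm only.
- *Hospital-treated events only, with usual care better covered* (h = 1, d_I = 0.6, d_C = 0.7): −0.5 points at 5% risk to −3 points at 30%.
- *Mixed events, usual care better covered for hospital visits* (p 10%, h 50%, q_I 10%, q_C 0, d_I 0.6, d_C 0.9): 0.10 × [0.5 × (−0.3) + 0.5 × 0.1] = −1.0 point.

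So the sign depends on the event type and on inputs that the documents do not supply. The described sources point in one direction only for hypotension, because only one arm's readings reach the study before month 6.

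**The case against.** The strongest objection is that the plan describes no route for falls or syncope in the intervention arm either. The Intervention section says that the pharmacist discusses side effects and that care plans, medication and lifestyle adherence are reviewed; it mentions no question on falling or fainting. Even for hypotension, the stated trigger for a call is uncontrolled pressure, and no low threshold or recording step is given. Usual-care patients are also offered a clinic appointment with a stroke neurologist or nurse practitioner, where events might come to light.

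Most of this stands. It removes any firm directional claim for falls and syncope and leaves only plausibility. It does not remove the asymmetry for hypotension, since low readings are visible to the study in one arm only. The clinic appointment is an offer and is not described as a study data source. Nor does the objection touch the omission: if neither arm has a described procedure, the declared outcomes are further from being measured.

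A reader might infer three stronger things:

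- *That the events will not be collected.* The case report forms are not in the documents, so the claim is only that collection is not described.
- *That the trial's safety comparison will be biased against the intervention.* No such comparison is planned, and for hospital-treated events usual care has one more form before month 6, so the imbalance could be small or run the other way.
- *That faulty safety estimates will feed the design of the larger trial.* Aim 2c and the statistical approach do not name safety among the quantities carried forward.

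**Conclusion.** The omission is established from the text: three declared safety outcomes are absent from the outcome list, the 6-month assessments and the analyses, and no common ascertainment is described. That conclusion needs no assumption beyond reading the plan as written.

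The second part is conditional. If a by-arm summary were made from the described sources, it would favour finding hypotension in the intervention arm and plausibly falls or syncope that led to no hospital visit. No magnitude can be given; the illustrative results run from −3 to +27 points purely according to the assumed inputs. The primary blood pressure analysis is unaffected. The point merits a short amendment because it changes what is collected and cannot be fully repaired afterwards.

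**What to change.** 1. **Primary Clinical Outcomes:** list hypotension, syncope and falls as safety outcomes, with definitions.
2. **Intervention, Usual Care and Outcome Assessments:** add the same two or three scripted questions (fainting, falls, symptomatic low blood pressure, since last contact) at 30 days, 90 days and 6 months in both arms. Existing contacts suffice: the 1-month video visit, the 3-month visit or iPad form and the 6-month visit for intervention; the 30- and 90-day calls and the 6-month visit for usual care. Preferably also use the 5-month visit and the 150-day contact, which cuts the longest recall from 90 days (90 to 180) to 60 (90 to 150). Ask about symptoms rather than readings, because only intervention patients are given a monitor.
3. **Statistical approach:** tabulate each outcome by arm with exact 95% intervals and the number asked at each time. With 50 patients, 0 events gives 0 to 7.1% and 5 events 3.3% to 21.8%, so the table will be descriptive. Base the comparison on the scripted answers only. Report telemonitored low readings for the intervention arm separately and descriptively.

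With truly equal detection the false difference is zero: at 10% risk and 0.9 detection in both arms, 50 × 0.10 × 0.9 = 4.5 expected patients in each.

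The cost is a slightly longer call or form: 2 to 3 questions × 3 contacts × 100 patients = at most 600 to 900 answers, or 800 to 1,200 with the fourth contact. Some asymmetry remains. The mode and the asker differ before month 6 (video or iPad with treating clinicians against telephone with a coordinator), and counselling or home monitoring may change what intervention patients report. If sensitivity differed by 10 points (assumed), the residual would be 0.05 × 0.10 = 0.5 points at 5% risk and 0.20 × 0.10 = 2 points at 20%.

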### **Costs, Reimbursement, and Compensation:**

Participants will receive 50 dollars for time and travel associated with the 6-month visit. They will also receive a parking voucher at for their 6 month visit.

### **Human Subject Issues:**

Consent will be obtained from patients and authorized representatives.

